1.5.2 BENEFIT-RISK ASSESSMENT

[REDACTED] is a brain penetrant PDE3, PDE4, PDE10 and PDE11 inhibitor. [REDACTED] has been marketed [REDACTED]. Recommended dosing is [REDACTED].

[REDACTED] Recommended dosing is [REDACTED] mg orally twice a day for asthma. In published studies of [REDACTED] with doses up to 100 mg/day, the most common AEs were headaches and GI effects (e.g., nausea,

diarrhea, and elevated liver enzymes). Rare cases of thrombocytopenia have also been reported. [REDACTED] has anti-inflammatory effects and is predicted to have therapeutic effects for patients with ASD-Phen1 because these patients are thought to have an inflammatory-specific phenotype. Beneficial activity has been reported in rodent models of inflammatory-based brain disorders.

[REDACTED] marketed in the United States [REDACTED] is a potent NKCC1 inhibitor that acts as a loop diuretic. It has been administered in doses of 0.5, 1, or 2 mg twice a day for up to three months in a randomized, double-blind, placebo-controlled trial of 88 children and adolescents (ages 2 to 18 years) with ASD [Lemonnier et al, 2017]. Statistically significant improvements on an autism rating scale (Childhood Autism Rating Scale [CARS]) and an autism severity scale (Social Responsiveness Scale, 2nd Edition [SRS-2]) were reported with [REDACTED] therapy over placebo among study completers. AEs were dose-related, the most common being hypokalemia, increased diuresis, loss of appetite, dehydration and asthenia. Six of 21 patients in the 2 mg twice a day group dropped out because of an AE, most frequently hypokalemia. Hypokalemia occurred generally at the beginning of treatment and improved gradually with oral potassium supplementation and potassium-rich foods. The [REDACTED] twice a day dose appeared to provide the best balance between safety and efficacy. To minimize the risk of hypokalemia, concomitant use of other loop diuretics (e.g., furosemide) will not be permitted during the study and electrolyte levels will be closely monitored. In the event of confirmed hypokalemia, potassium supplementation will be prescribed.

The 4-week rat and dog toxicology packages support the current clinical trial starting with a combination of [REDACTED] twice a day and [REDACTED] twice a day in cohort 1, followed by [REDACTED] twice a day and [REDACTED] twice a day in cohort 2. The pivotal toxicity studies performed in rats and dogs have shown that dog is the most sensitive species to STP1 treatment: the NOAEL was 3 mg/kg/day in male dogs which represents a 5-fold safety margin based on allometric scaling.

[REDACTED] has immunomodulatory and anti-inflammatory properties and, as such, should not be taken while an acute infection is ongoing. Therefore, patients with active infection, including (but not limited to) bacterial, fungal or viral infection, will not be included in the trial. Rare cases of thrombocytopenia have been reported with the use of [REDACTED] even though not expected at the dose levels used in this study and the short treatment duration, platelet count will be monitored throughout the study and patients with history of thrombocytopenia within the past year will not be included in the study. The use of other medication that could worsen possible thrombocytopenia will be used with precaution. [REDACTED] is predominantly cleared by CYP3A4 metabolism with to a lesser extent other CYP450 pathways (see Section 1.3.2). In order to avoid interference with the PK of STP1, moderate or strong CYP3A4 inhibitors (e.g., ketoconazole) are excluded. As a potent loop diuretic, [REDACTED] may trigger hypokalemia and hypotension. Changes in electrolyte levels and blood pressure (including orthostatic blood pressure [BP]) will be monitored at each post-dose study visit and other loop diuretics will be prohibited. PK drug-drug interactions between [REDACTED] are not expected since both compounds are metabolized by different pathways. Both drugs are inhibitor of BCRP transporter at subclinically relevant levels, but the effect of drug combination on BCRP is unknown and drugs that are substrate of BCRP should be used with caution during this clinical trial. It is

possible that because [REDACTED] is a diuretic, an effect on the renal clearance of [REDACTED] may be observed, leading to a reduction in [REDACTED] plasma level. Urinary drug levels of [REDACTED] will be assessed in this study to evaluate potential effects of [REDACTED] clearance.

Overall, the risk to patients with ASD-Phen1 treated with STP1 is considered small. There is limited or no direct benefit expected for the patients enrolled in this trial, designed to assess safety, tolerability and PK of 2 doses of STP1 given twice a day for 2 weeks. However, the unmet medical need for effective treatment in Autism is enormous. Given the potential of STP1 to significantly improve the identified dysregulated biological pathways in ASD-Phen1, the potential benefit for future patients (including pediatrics) would be significant.

2. OBJECTIVES OF THE STUDY

2.1 PRIMARY OBJECTIVE

The primary objective of the study is:

- To determine the safety and tolerability of 2-week twice a day (6 hours apart) treatment with STP1 (combined oral doses of [REDACTED]) in adult patients with ASD-Phen1.

2.2 SECONDARY OBJECTIVE

The secondary objective of the study is:

- To determine the plasma PK of multiple dosing and to determine the concentration in the urine of [REDACTED] when given orally in combination, as STP1, for 2 weeks.

2.3 EXPLORATORY OBJECTIVES

The exploratory objectives of this study are as follows:

- To evaluate the effect of a 2-week treatment with STP1 compared to placebo on cognition as assessed by subtests of the [REDACTED] and the Test of Attentional Performance for Children (KiTAP) test battery.
- To evaluate the effect of a 2-week treatment with STP1 compared to placebo on maladaptive behavior as assessed by the Aberrant Behavior Checklist–Community (ABC-C).
- To evaluate the effect of a 2-week treatment with STP1 compared to placebo change in the context of autism as measured by the change in the Ohio Autism Clinical Impression Scale (OACIS) change.
- To evaluate the effect of a 2-week treatment with STP1 compared to placebo on the Children Sleep Habit Questionnaire (CSHQ) scores.
- To evaluate the effect of a 2-week treatment with STP1 compared to placebo on the Clinical Global Impressions-Severity (CGI-S) scale, also reflected by the Clinical Global Impressions-Improvement (CGI-I) scale.
- To evaluate the effect of a 2-week treatment with STP1 compared to placebo on brain electrophysiology parameters as measured by electroencephalogram (EEG).
- To evaluate the effect of a 2-week treatment with STP1 compared to placebo on gaze aversion and social interest by assessing eye tracking tasks.
- To evaluate the effect of a 2-week treatment with STP1 compared to placebo on Lactate/Pyruvate ratio (L:P).

3. INVESTIGATIONAL PLAN

3.1 STUDY DESIGN

This is a randomized, double-blind, placebo-controlled, parallel-group, 2-dose ascending study cohort (first and second), to assess the safety, tolerability and PK of 2-week treatment with STP1 in adult patients with ASD-Phen1.

3.1.1 OVERVIEW OF STUDY DESIGN

[Figure 2](#) gives an overview of the study design. If eligible, the first dose cohort (8 patients) will be randomized and allocated to one of two groups with a 3:1 ratio:

- One group will receive [] mg oral twice a day (6 hours apart) oral [] and [] mg oral twice a day (6 hours apart) oral [] (STP1 dose 1, N=6).
- One group will receive matching oral placebo twice a day (6 hours apart) (N=2).

Once the first dose cohort (8 patients) finishes the 2 weeks of STP1 treatment and the 2 weeks of follow up, a DSMB will evaluate the safety and tolerability data to decide whether the dose of [] can be increased as planned to [] mg, or the study should be modified or be stopped.

[figure not shown]
If the analysis supports the start of the next dose level, up to 8 additional eligible patients will be assigned to the next dose level (patients that participated in the first cohort maybe allowed to participate in the second if no safety concern):

- One group will receive [] mg oral twice a day (6 hours apart) oral [] and [] mg oral twice a day (6 hours apart) oral [] (STP1 dose 2, N= up to 6).
- One group will receive matching oral placebo twice a day (6 hours apart) (N= up to 2).

For each dose cohort, the total duration of the study for each patient will be up to 6 weeks divided as follows:

- A screening phase of 2 weeks (from Day -14 to Day -1).
- A double-blind treatment phase of 2 weeks (from Day 1 to Day 14).
- A follow-up phase of 2 weeks after treatment discontinuation (from Day 15 to Day 28).

Figure 2 Overview of Study Design

For STP1 dose 2: N= up to 2 placebo and up to 6 STP1 dose 2

3.1.2 STOPPING RULES

Study Stopping rules

During and after the administration of STP1, the patient will be closely monitored for clinically significant signs and symptoms potentially related to the study drugs (ibudilast and bumetanide), in particular for signs and symptoms GI and dehydration and for clinically significant changes in the electrocardiogram (ECG). Any AE should be followed up until resolution. If not resolved, STALICLA shall be contacted and the patient may be considered to withdrawn from the trial depending on the severity of the event/s.

The DSMB will perform reviews of safety data throughout the study.

Enrolment in the study will be placed on hold and no further dosing will occur pending a full safety review if:

- One fatal or life-threatening SAE occurs, that is considered by the investigator as potentially or possibly related to SPT1 and later confirmed the patient received investigational medicinal product (IMP).
- STALICLA, investigators and/or the DSMB considers that the number and/or severity of AEs, abnormal safety monitoring tests or abnormal laboratory findings justify putting the study on hold. Examples are:
 - One severe systemic-related reaction occurs and does not resolve within 24 hours.
 - Three or more similar severe AEs occur as defined by the Common Terminology Criteria for Adverse Events (CTCAE v5.0), which are judged related to STP1.

- If 2 patients at any dose level discontinue treatment due to changes in vital signs, ECG intervals or findings on continuous ECG monitoring no further patients will be enrolled at this dose level pending review by DSMB.

The DSMB can recommend (i) for the study to continue without amendment, (ii) to continue the study with modifications to the protocol or (iii) to stop the study.

The study may continue after the safety review, if the DSMB and STALICLA agree it is safe to proceed.

Individual stopping rules

If a patient experiences an AE following administration of study drug (i.e., post-treatment) that is judged to be related to the study drug, and is graded as severe or SAE, no further doses of study drug will be administered.

If a patient experiences an AE that is judged to be related to the study drug, and is graded as mild or moderate, the patient may receive a further dose of study drug following discussion with the investigator and sponsor, dependent on the nature of the AEs reported. Expected transient GI pain requiring 48 hours stop and not resuming with reinitiation of treatment is commonly observed. The number of subjects reporting similar AEs and reports of the same or similar AEs in a patient, will form part of the assessment to determine if patients should be re-challenged.

Changes in vital signs and ECG intervals

Patients will be discontinued if after repeated measurements, have pulse/heart rate, blood pressure or ECG interval measurements that fulfil one or more of the criteria listed below.

Vital signs

- Pulse/heart rate <40 or >120 beats per minute (BPM)
- Systolic BP <90 or >180 mm Hg
- Diastolic BP <50 or >100 mm Hg

Laboratory tests

- Severe hypokalemia (defined as less than 2.5 mEq/L) or persistent hypokalemia despite potassium supplementation
- Thrombocytopenia is defined as meeting one or both criteria:
 - Platelet count below $150 \times 10^9/L$ (or 150.000 platelets per microliter (mcL))
 - Platelet count drop of $\geq 50\%$ compared to baseline
- Severe drug-induced liver injury (DILI).
- Dehydration and orthostasis (defined by a fall in systolic blood pressure over 20 mm Hg or a fall in diastolic pressure over 10 mm Hg within 3 minutes of standing).

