Exclusion Criteria	
Individuals meeting any of the following criteria will not be included in the trial:
 
 1. Patients with an identified genetic cause of ASD in their medical record will be excluded from the study. 2. History of traumatic head injury, cerebrovascular disorder, congestive heart failure, hepatic or renal disease. 3. Thrombocytopenia (platelet count < 100 000 mm³) within 1 year prior to the screening visit. 4. Diabetes (type 1 diabetes mellitus or uncontrolled type 2 diabetes mellitus) or latent autoimmune diabetes of the adult (LADA). 5. Use of prohibited medications (Section 4.5.1) or herbal remedies within 2 weeks prior to randomization, or 5 half-lives (whichever is longer). 6. Alcohol and/or substance abuse/dependence within 12 months prior to screening. 7. A significant risk for suicidal behavior, in the opinion of the investigator and as assessed by the Columbia Severity Rating Scale (C-SSRS) or the simplified version adapted from the Columbia Classification Algorithm for Suicide Assessment (C-CASA). 8. Use of antioxidant supplements and/or vitamins within 2 weeks prior to randomization. 9. Initiation of, or a major change in psychological/behavioral intervention within 4 weeks prior to randomization. 10. Patient with any active infection, including but not limited to the following: 
 o Bacterial infection; or o Fungal infection; or

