	
○ Positive result at screening for hepatitis B virus (HBV), hepatitis C virus (HCV), or human immunodeficiency virus (HIV)-1 and severe acute respiratory syndrome coronavirus 2 (SARS-CoV-2).11. Episode of fever (i.e., $\geq 100.5^{\circ}\text{F}$ or 38.0°C) or clinically significant illness without fever (as judged by the investigator), within 10 days before Day 1.12. Sustained resting systolic blood pressure (SBP) <80 mmHg or diastolic blood pressure (DBP) <40 mm Hg or a drop in SBP of ≥ 20 mm Hg, or in DBP of ≥ 10 mm Hg, or patient experiencing lightheadedness or dizziness during the orthostatic recordings.13. Clinically relevant electrocardiogram (ECG) abnormalities; QTcF (Fredericia's correction) >450 ms (at screening or Day 1 pre-dose).14. Confirmed clinically significant abnormal laboratory test results at screening (lactate and pyruvate not included) other than the conditions related to ASD-Phen1.15. Patients with any active clinically significant disease (i.e. gastroenterological, endocrinological, renal, respiratory, cardiovascular, hepatic dysfunction, immunological or hematological disease) that following the judgment of the investigator may interfere with the conduct of the study, other than the conditions related to ASD-Phen1.16. Patients with any history of malignancy of any organ system (other than localized basal cell carcinoma of the skin), treated or untreated, within the past 5 years, regardless of whether there is evidence of local recurrence or metastases.17. Pregnant (confirmed by laboratory testing) or lactating female patient.18. Participation in an investigational drug study within 30 days or 5 times its half-life, whichever longer, prior to randomization.

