4.2.3 EXCLUSION CRITERIA

Study patients who meet any of the following criteria will not be included in the study:

1. Patients with an identified genetic cause of ASD in their medical record will be excluded from the study.
2. History of traumatic head injury, cerebrovascular disorder, congestive heart failure, hepatic or renal disease.
3. Thrombocytopenia (platelet count <100,000 mm³) within 1 year prior to the screening visit.
4. Diabetes (type 1 diabetes mellitus or uncontrolled type 2 diabetes mellitus) or latent autoimmune diabetes of the adult (LADA).
5. Use of prohibited medications ([Section 4.5.1](#)) or herbal remedies within 2 weeks prior to randomization, or 5 half-lives (whichever is longer).
6. Alcohol and/or substance abuse/dependence within 12 months prior to screening.
7. A significant risk for suicidal behavior, in the opinion of the investigator and as assessed by the Columbia Severity Rating Scale (C-SSRS) or the simplified version adapted from the Columbia Classification Algorithm for Suicide Assessment (C-CASA).
8. Use of antioxidant supplements and/or vitamins within 2 weeks prior to randomization.
9. Initiation of, or a major change in psychological/behavioral intervention within 4 weeks prior to randomization.
10. Patient with any active infection, including but not limited to the following:
 - Bacterial infection; or
 - Fungal infection; or
 - Positive result at screening for hepatitis B virus (HBV), hepatitis C virus (HCV), or human immunodeficiency virus (HIV)-1 and severe acute respiratory syndrome coronavirus 2 (SARS-CoV-2).
11. Episode of fever (i.e., ≥100.5°F or 38.0°C) or clinically significant illness without fever (as judged by the Investigator), within 10 days before Day 1.
12. A SBP <80 mm Hg or a (DBP) <40 mm Hg or a drop in SBP of ≥20 mm Hg, or in DBP of ≥10 mm Hg, or patient experiencing lightheadedness or dizziness during the orthostatic recordings.
13. Clinically relevant ECG abnormalities; QTcF (Fredericia's correction) >450 ms (at screening or Day 1 pre-dose).
14. Confirmed clinically significant abnormal laboratory test results at screening (lactate and pyruvate not included) other than the conditions related to ASD-Phen1.
15. Patients with any active clinically significant disease (i.e. gastroenterological, endocrinological, renal, respiratory, cardiovascular, hepatic dysfunction,

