4.7 PATIENT, STUDY, AND SITE DISCONTINUATION

4.7.1 PATIENT DISCONTINUATION

The investigator has the right to discontinue a patient from STP1 or withdraw a patient from the study at any time. In addition, patients have the right to voluntarily withdraw from the study at any time for any reason. Reasons for discontinuation of STP1 or withdrawal from the study may include, but are not limited to, the following:

- Patient withdrawal of consent at any time.
- Any medical condition that the investigator or sponsor determines may jeopardize the patient's safety if he or she continues in the study.
- Investigator or sponsor determines it is in the best interest of the patient.
- Patient non-compliance.

Patients who fulfill the criteria described in the Stopping Rules section (as defined in [Section 3.1.2](#)) should be discontinued from the study.

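### Entry limits for blood pressure and platelets are looser than the stopping limits, so unless the investigator excludes on judgment, a patient can enrol already at a discontinuation limit

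*Protocol*

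**What the plan says.** **Entry.** Exclusion 12 in Protocol 4.2.3 removes "A SBP <80 mm Hg or a (DBP) <40 mm Hg", plus an orthostatic clause. The synopsis gives the same numbers as "Sustained resting systolic blood pressure (SBP) <80 mmHg or diastolic blood pressure (DBP) <40 mm Hg". Exclusion 3 reads "Thrombocytopenia (platelet count <100,000" per mm3 and looks back one year from screening; the synopsis uses the same number. Exclusions 14 and 15 let the investigator keep out a patient with a clinically significant laboratory abnormality or an active clinically significant disease, hematological disease included. Neither gives a platelet or blood pressure number.

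**Stopping.** Section 3.1.2 discontinues patients whose repeated values meet "Systolic BP <90 or >180 mm Hg" or "Diastolic BP <50 or >100 mm Hg". Its laboratory list adds platelets below 150 x 10^9/L ("or 150.000 platelets per microliter (mcL") or a fall of at least 50% from baseline, and either one is enough. The mandatory sentence (*will*) names only pulse or heart rate, blood pressure and ECG intervals. Section 4.7.1 covers the rest: it takes "Patients who fulfill the criteria described in the Stopping Rules section" and says that they *should* leave the study.

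**Related text.** Section 5.1.3 uses the same platelet number to define an adverse event of special interest (AESI). Section 1.5.2 says that patients with thrombocytopenia in the past year are kept out, but gives no number.

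**The concern.** Where a plan sets both an entry limit and an absolute stopping limit for one measurement, the entry limit should be at least as strict. Otherwise a patient can qualify and call for removal on the same unchanged value. The stop then says nothing about the drug, yet it uses up a place in a very small study.

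Platelets are the more awkward case. Appendix 1 schedules hematology at screening and next on Day 7, with none on Day 1. A patient with a steady count of 130 would take about six days of a combination in which one component has been linked to rare thrombocytopenia. That patient could then reach the stopping limit, and the AESI number, with nothing having changed. Whether this counts as an adverse event is unclear. Section 5.3.5.8 records a preexisting condition only if it worsens, whereas 5.3.5.4 includes a laboratory result that changes study treatment.

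Blood pressure is measured again before dosing on Day 1, and under 4.4.2 the first dose waits for that check and for confirmed eligibility. A stable SBP of 85 still passes eligibility, but it should usually be seen to be at the stopping limit. If acted on then, the cost is a withdrawal before dosing, with the randomization number reused (SAP 1.3.1).

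**Working it through.** The plan states no figure to reproduce. The check compares thresholds and counts doses.

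**1. Overlap.** A value is in the gap if it is not below the entry limit but is below the stopping limit. For platelets, 100,000/mm3 = 100 x 10^9/L.

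| Measure | Excluded below (4.2.3) | Stopping limit below (3.1.2) | Eligible but at the limit | Width |
|---|---|---|---|---|
| SBP, mm Hg | 80 | 90 | 80-89 | 90 - 80 = 10 |
| DBP, mm Hg | 40 | 50 | 40-49 | 50 - 40 = 10 |
| Platelets, 10^9/L | 100 | 150 | 100-149 | 150 - 100 = 50 |

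**2. Is there an exemption?** The subsection heading in 3.1.2 speaks of changes, but the limits beneath it are absolute. Requiring repeated measurements removes transient lows, not stable ones. For platelets, the 50% fall is an alternative to the 150 limit, not an added condition. Neither 3.1.2, 4.7.1 nor 5.1.3 exempts a value present at baseline.

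**3. The orthostatic limits do not share the problem.** Entry excludes falls of at least 20/10 mm Hg; stopping applies to falls over 20/10.

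**4. Doses before the Day 7 draw.** Dosing is twice daily on Days 1-13 and once on Day 14: 13 x 2 + 1 = 27. Days 1-6 give 6 x 2 = 12 doses before the Day 7 pre-dose sample, and 12/27 = 44%. With the one-day visit window the count is 5 x 2 = 10 to 7 x 2 = 14. Appendix 1 footnote c implies an afternoon dose on Day 14; on that reading the share is 12/28 = 43%.

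**5. What a Day 7 stop costs.**
- Safety population: kept, since one administration suffices (Protocol 6.3.1, SAP 2.2).
- PK population: kept, with the Day 1 profile and the Day 7 pre-dose sample (Protocol 6.3.3).
- Day 14 PK profile: lost.
- Exploratory population: lost, because it requires the full course (SAP 2.2).
- Replacement: allowed (Protocol 4.7.1.1).

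**6. After the fix.** With entry limits of 90, 50 and 150, no value is both eligible and below a stopping limit.

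**The case against.** The strongest reply is that the mismatch rarely matters in practice. Section 4.6.2.1 requires screening results to be reviewed before eligibility is confirmed, and uncertain abnormal results to be repeated. The investigator would therefore see a count of 120, and the protocol's own 150 definition together with exclusions 14 and 15 gives grounds to refuse entry. This stands in part: the value is known and can be acted on. But nothing obliges exclusion, and a count judged not clinically significant remains eligible.

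The platelet stop is also less firm than the blood pressure stop, since it rests on the *should* in 4.7.1, and the must-discontinue list in 4.7.1.1 names neither measure. That stands, and it lowers confidence.

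Other stopping limits (heart rate, high blood pressure, severe hypokalemia) have no numeric entry limit at all. True, but here the plan does set a number at entry, and sets it looser than the stopping limit.

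A reader might infer more than the documents support:
- *That low platelets pass into dosing unnoticed.* They do not, because screening results are reviewed.
- *That one such patient removes a third of the minimum of 3 at the highest dose.* The synopsis asks for 3 patients exposed, and a patient stopped on Day 7 has been exposed.
- *That all multiple-dose PK is lost.* The Day 7 pre-dose sample remains, and 3.2.1 expects steady state of one component after 4 days.
- *That low baseline pressures could trigger the enrolment hold for two vital-sign discontinuations at a dose level.* That rule speaks of changes, and stable low pressure should usually be seen before dosing. The chance of at least 2 of 8 patients being in the gap also depends wholly on an assumed frequency: 1.0%, 5.7%, 18.7% or 34.3% if 2%, 5%, 10% or 15% of patients were in it. The documents give no such frequency.

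**Conclusion.** The point holds as a minor inconsistency, with medium confidence, and is worth making as a cheap improvement. Exclusions 12 and 3 are looser than the absolute limits in 3.1.2 by 10 mm Hg systolic, 10 mm Hg diastolic and 50 x 10^9/L platelets, with no baseline exemption. A stable value in any of these bands can be enrolled, unless the investigator excludes on judgment, and already calls for discontinuation: firmly for blood pressure, through 4.7.1 for platelets.

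The practical cost is limited. For platelets, it is about 12 of 27 doses and then a possible stop unrelated to any change, with loss of the Day 14 profile and of Exploratory membership for that patient. In a full active arm of 6, one patient is 1/6 = 17% of the planned Day 14 profiles before any replacement. For blood pressure, the usual cost is an avoidable withdrawal before dosing; a post-dose stop would need a borderline value or one not acted on.

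This assumes that the value is stable, that the investigator does not exclude, and that 3.1.2 and 4.7.1 are applied as written. No claim is made about how many patients fall in these bands.

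**What to change.** In Protocol 4.2.3 and the synopsis:
- Change the blood pressure limits in exclusion 12 to SBP below 90 or DBP below 50 mm Hg on repeated resting measurement, and keep the orthostatic clause.
- Add to exclusion 3 a platelet count below 150 x 10^9/L at screening.
- Leave the FDA-requested 150 x 10^9/L AESI and stopping limit as it is.

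This rewords two criteria in two places and needs no new test, because both values are already measured at screening. The price is possibly a few more screen failures in a narrowly defined population, among patients whom the stopping rules would call to remove anyway. Defining the stops relative to baseline would also remove the conflict, but it would mean rewriting safety limits, including the one set at FDA request. Raising the entry limits is simpler.
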